11 CLINICAL MONITORING

11.1 Site Monitoring Plan

Subcontractor, Westat will provide monitoring and safety oversight for the SCOUT Study for all aspects of clinical site and laboratory monitoring, pharmacy auditing, quality control and adverse event reporting. Their responsibilities in this capacity include development of a site monitoring plan; monitoring of sites for protocol adherence, competence of staff, observance of quality assurance procedures; proper storage and security of study product, maintenance of records and subject eligibility; inspection of IRB approval documents; review of subject records for protocol adherence, accuracy, completeness and source document verification; meetings with study staff to review findings, problems, deficiencies and possible solutions; and reporting through CHOP to the DMID Project Officer to summarize key findings, deficiencies and corrective actions.

Westat site monitors will visit the CHOP and PITT research sites to review a selected proportion of the individual subject records, including consent forms, CRFs and supporting source documentation to ensure protection of study subjects, compliance with the protocol, and accuracy and completeness of records. Eligibility will be confirmed for 100% of subjects; and full chart review will be performed for five percent of subjects, unless performance issues indicate that more extensive review is advisable. Regulatory files will also be inspected to ensure that regulatory requirements are being followed. The clinical monitoring plan will be reviewed and approved by the DMID. In addition, DMID will be sent all monitoring reports and that DMID retains the right to assess the quality of monitoring at any time during the study.

Westat site monitors will also visit the CHOP and PITT study product area to review the overall study product management system, including receipt, storage, disposition and accountability of study products.

The site investigators and study teams will make study documents (e.g. consent forms, case report forms) and pertinent hospital and clinical records available for inspection by the local IRB, the site monitors, the FDA, NIAID, the Office of Human Research Protection (OHRP), or the sponsor’s designee for confirmation of the study data. Per DMID Source Documentation Standards for DMID clinical studies, v2, March 16, 2004 - if any original records/source documents cannot be made available to monitors for verification of data collected, a “Certified Copy” of the records can be made and kept as part of a separate research record.

12 STATISTICAL CONSIDERATIONS

12.1 Study Objectives

Primary Objective:

To determine if halting antimicrobial therapy in subjects who have exhibited clinical improvement 5 days after starting antibiotic therapy (short course therapy) have the same failure rate (symptomatic UTI) through TOC (visit Day 11-14) as subjects who continue to take antibiotics for an additional 5 days (standard course therapy).

Secondary Objectives:

To determine if short-course therapy compared to standard course therapy results in similar numbers of children experiencing a recurrent infection (relapse and reinfection).

To determine if short-course therapy compared to standard course therapy results in similar numbers of children with asymptomatic bacteriuria.

To determine if short-course therapy compared to standard course therapy results in similar numbers of children with gastrointestinal colonization of antimicrobial resistant *Escherichia coli* (*E. coli*) and *Klebsiella pneumoniae* (*K. pneumoniae*).

To determine if short-course therapy compared to standard course therapy results in similar numbers of children with clinical symptoms that may be related to a UTI.

To determine if short-course therapy compared to standard course therapy results in similar numbers of subjects with positive urine cultures prior to or at the TOC visit.

Sub-Study Objectives:

To determine if *E. coli* and *K. pneumoniae* recovered from 2 or 3 stool cultures are more likely to be members of disease-associated subgroups within their respective species (*E. coli* phylogroups B2 and D, *K. pneumoniae* clusterKpl)

To determine if treatment-susceptible strains recovered from cultures during treatment (culture #1 for 5-day arm; cultures #1 or #2, 10-day arm) are more likely to be members of disease-associated subgroups;

To determine if treatment-resistant strains of either species are more likely than treatment susceptible strains to be recovered from cultures during treatment

To determine the overall prevalence of colonization with carbapenem-resistant Enterobacteriaceae (overall and for specific pathogens) in ambulatory children after completion of treatment for UTI

To compare the overall biodiversity of the gut microbial community, as measured by culture-independent marker gene sequencing at each follow-up visit following short-course and standard-course antibiotic exposure.

To compare the overall fraction of gut microbiome community represented by gammaproteobacteria measured by culture-independent marker gene sequencing at each follow-up visit following short-course and standard-course antibiotic exposure.

To compare the average ecological similarity between microbial communities within and between treatment groups at each follow-up following short-course and standard-course antibiotic exposure.

To describe the breadth of bacteria present in the stool of children receiving therapy for a urinary tract infection. These data will allow for comparison of aerobic bacteria stool composition in these children and present an opportunity to contrast them to similar data available from other pediatric patient populations.

12.2 Sample Size Considerations

The primary aim of this study is to determine if halting antimicrobial therapy in subjects that show clinical improvement 5 days after starting antibiotic therapy (short course therapy) is as effective as continued therapy through day 10 (standard course) as determined by treatment failure rate (symptomatic UTI) through TOC visit Day 11-14 (6-9 days after starting per protocol therapy).

The treatment failure rate under the standard of care, R_0 , is expected to be 5%. This estimate is based on data from previously published studies [43, 47]. The power and sample size calculations are based on the assumption that treatment failure under the short-course therapy, R_{SC} , will range from 5% to 9%.

In the non-inferiority test, on which power and sample size are based, the null hypothesis that short-course therapy is inferior to standard-of-care therapy is tested against the alternative that short-course therapy is non-inferior. That is, $H_0: R_{SC} > R_0 + \delta$ is tested against $H_a: R_{SC} \leq R_0 + \delta$, where δ is the “interval of equivalence,” the range

in which the treatment failure rates of the two therapies would be considered clinically equivalent. We believe that an interval of equivalence of 5% would be clinically acceptable; a success rate of 95% for the standard-of-care therapy group when compared to 90% for the short-course therapy group. For all power and sample size calculations, the significance level (chance of incorrectly failing to reject the null hypothesis) is $\alpha = 0.05$.

12.3 Planned Interim Analyses

An interim analysis for the primary outcome measure will be performed once half the subjects have enrolled (to get 336 subjects who are evaluable for the primary endpoint). This analysis will test the null hypothesis that the treatment failure rate under short course therapy is equal to (or less than) that of standard therapy against the alternative hypothesis that the failure rate under short-course therapy is greater than using standard-of-care therapy. This test will be one-sided with $\alpha = 0.05$. The endpoint for this analysis will be the treatment failure rate. The statistical test will be a one-sided test of the hypothesis of equal failure rates between the two study arms.

As part of the interim data analyses, conditional power estimates may be made. The conditional power analysis is a re-assessment of the power given the results of the study to date. Large, early differences imply high conditional power; but small differences in the early part of a study may suggest lower power than initially expected.

The methods for the planned statistical interim analysis will be described and justified in the Statistical Analysis Plan (SAP), including the timing of the interim analyses (i.e., when half of the subjects have completed the study), the scope of the interim analysis including a description of which endpoints will be analyzed (i.e., efficacy analysis of the primary endpoint), and the methods or statistical tests that will be used in the analyses. Note that since the interim analysis is for superiority of standard therapy and the final efficacy analysis is for non-inferiority of short-course therapy, there is no impact of the interim analysis on the Type I error of the final efficacy analysis and thus no adjustments to the significance level are required. The SAP will be written prior to the interim analysis.

12.4 Final Analysis Plan

General Design: The data analysis will consist of several parts. First, descriptive and baseline statistics will be generated for outcome measures for the purpose of describing the study population and comparing the two study arms at baseline. Second, the primary and secondary analyses will be conducted. Finally, primary and secondary outcome measures will be compared between various subgroups of the study participants to assess potential interactions with treatment effects. Details will be provided in the

statistical analysis plan (SAP) which will be finalized prior to the interim analysis. A general description of the planned approach is provided below.

Study Endpoints:

The primary outcome measure is:

Comparison of efficacy, based on symptomatic UTI as assessed at the TOC visit (Day 11-14), between short-course and standard-course of antibiotics.

The secondary outcome measures are:

Comparison of number of subjects that have a recurrent infection (includes a relapse UTI or a reinfection) at any time after the TOC visit (Day 11-14), following a short-course versus standard-course of antibiotics.

Comparison of the number of subjects that become colonized with antimicrobial resistant *Escherichia coli* (*E. coli*) and *Klebsiella pneumoniae* (*K. pneumoniae*) in the gastrointestinal tract as assessed through Day 24-30, following short-course (5-day) versus standard course (10-day) of antibiotics.

Comparison of the number of subjects with asymptomatic bacteriuria following short-course (5-day) versus standard course (10-day) of antibiotics.

Comparison of the number of subjects with clinical symptoms that may be related to a UTI following short-course (5-day) versus standard course (10-day) of antibiotics.

Comparison of the number of subjects with positive urine culture prior to or at the TOC visit following short-course (5-day) versus standard course (10-day) of antibiotics.

The sub-study outcome measures are:

Seattle R21

Presence of *E. coli*, presence of *K. pneumoniae*

Sub-types of *E. coli* (0=phylogroups A or B1, 1=phylogroups B2 or D), sub-types of *K. pneumoniae*

Presence of treatment-susceptible *E. coli*, presence of treatment-susceptible *K. pneumoniae*

Presence of treatment-resistant *E. coli*, presence of treatment-resistant *K. pneumoniae*

Carbapenem-resistant Enterobacteriaceae

Presence of carbapenem-resistant Enterobacteriaceae (overall and for specific pathogens).

Microbiome pilot study

Comparison of the overall biodiversity of the gut microbial community, as measured by culture-independent marker gene sequencing at each follow-up visit following short-course and standard-course antibiotic exposure.

Comparison of overall fraction of gut microbiome community represented by gammaproteobacteria measured by culture-independent marker gene sequencing at each follow-up visit following short-course and standard-course antibiotic exposure.

Comparison of average ecological similarity between microbial communities within and between treatment groups at each follow-up following short-course and standard-course antibiotic exposure.

Spectrum of Stool Bacteria

Description of the bacteria present on the aerobic stool cultures obtained at each the three study time points.

Descriptive Analysis: Standard descriptive statistics will be used to describe subjects' baseline characteristics at the time of enrollment, as well as study outcome measures overall and within each treatment group. Summary statistics such as means, standard deviations, medians, and ranges will be produced for continuous variables. Frequency counts and percentage will be generated for describing variables that are dichotomous or polytomous in nature. The balance of baseline measures (i.e., at the time of enrollment) between short-course therapy group and standard-of-care therapy group will be compared using two-sample tests, including *t*-tests, the Mann-Whitney test, chi-square tests, and so forth, as appropriate.

Primary Analysis / Efficacy Analysis: The primary analysis will follow Intent-to-Treat (ITT) principles, with subjects analyzed according to randomized treatment assignment. In addition, a “per-protocol” analysis will be performed; the per-protocol analysis would include only subjects who were adherent to their assigned study regimen and completed 80% or more of the prescribed dose. All subjects taking at least one dose of study drug(s) who have been evaluated for treatment success at TOC visit or have failed treatment prior to TOC will be included in the ITT analysis (see the table below). The primary analysis will be a non-inferiority test comparing the number of symptomatic UTIs at the TOC visit between two treatment arms along with the 5% equivalence interval. The confidence interval of the difference in symptomatic UTI rates between the short-course and standard-of-care therapies will be calculated to evaluate whether this difference is less than or equal to the equivalence interval. This will be a one-sided test with $\alpha = 0.05$. Subjects with asymptomatic bacteriuria or who are asymptomatic with a

positive culture including pyuria will NOT be considered treatment failures for the primary outcome measure.

Table 9: SCOUT Study product Dosage Adherence

Antibiotic Drug	Antibiotic Dosage	80% of Expected Doses
Trimethoprim-Sulfamethoxazole (TMP-SMX)	8 mg/kg/day of Trimethoprim in 2 divided doses, Max 160mg BID Trimethoprim	Eight doses
Amoxicillin-Clavulanate*	45 mg/kg/day in 2 divided doses, Max 875 mg Q12H	Eight doses
Cefixime	8 mg/kg/day in 1 dose, Max 400 mg	Four doses
Cephalexin	50mg/kg/day in 3 divided doses	Twelve Doses

*Amoxicillin-clavulanate is no longer included as a study antibiotic, but subjects randomized to this treatment prior to its removal must have taken at least eight doses to be included in the per-protocol analysis.

Secondary Analysis:

The secondary outcome measures of this trial are provided above. A difference between the two arms with regards to asymptomatic bacteriuria, presence of clinical symptoms, and negative urine culture is not expected. No difference will mean that shorter courses of antibiotics for treatment are not inferior to long courses in eradicating bacteria from the urinary tract as well as impacting clinical symptoms. This analysis will be a conventional test for efficacy and will consist of a straightforward two-sample test for a difference between proportions, using a two-sided chi-square test at significance level of .05.

Sub-study Analysis:

Seattle Children’s Hospital R21

As previously noted, patient stool samples will be collected on 3 occasions. For primary analysis, cross-sectional analysis will be performed, i.e. looking at samples from one occasion at a time.

For each occasion, the following proportions will be summarized:

- 1) Among all patients, proportion of patients with *E. coli* detected, proportion of patients with *K. pneumoniae* detected, and same proportions within each treatment arm.
- 2) Among patients with *E. coli* detected, proportions of sub-type 0 or sub-type 1; among patients with *K. pneumoniae* detected, proportions of the two sub-types, and same proportions within each treatment arm.
- 3) Among patients with *E. coli* detected, proportions of treatment-susceptible *E. coli*; among patients with *K. pneumoniae* detected, proportion of treatment-susceptible *K. pneumoniae*; and same proportions for different treatment arms.
- 4) Among patients with *E. coli* detected AND treatment-susceptible, proportions of sub-type 1; among patients with *K. pneumoniae* detected AND treatment-susceptible, proportions of sub-type 1; and same proportions for different treatment arms
- 5) Among patients with *E. coli* detected proportion of treatment-resistant *E. coli*; among patients with *K. pneumoniae* detected, proportion of treatment-resistant *K. pneumoniae*; and same proportions within different treatment arms.

After obtaining the proportions listed in (2) above, a binomial test will be used to determine whether the proportion of *E. coli* sub-type 1 (phylogroups B2 and D) is significantly larger than 50%. A chi-square test will also be used to test the differences in proportions of sub-type 1 across treatment arms. In addition, a multivariable logistic regression on presence of sub-type 1 strains will be conducted. The same approach will be used for *K. pneumoniae* sub-type 1.

For culture #1 (5-day treatment arm), or culture #1 or #2 (10-day treatment arm), the proportions of sub-type 1 will be tested using a binomial test, then a logistic regression will be used to examine the association between presence of sub-type 1 strains and treatment arms.

A chi-square test will be used to examine the difference in proportions estimated in (3) and (5) above. Logistic regression models will also be used for analysis.

Microbiome pilot study

We will preprocess all marker-gene microbiome sequencing data using the Quantitative Insights Into Microbial Ecology (QIIME) software package [PMID: 20383131]. This will include performing sequence quality filtering and demultiplexing of reads to separate sequences by sample. For taxonomic marker gene and RNA-Seq sequences, we will stitch overlapping paired-end reads together after demultiplexing using PANDAseq [PMID: 22333067]. We will then map marker gene reads to 97% operational taxonomic units (OTUs) using the Greengenes [PMID: 22134646] reference database and the USEARCH [PMID: 20709691] reference mapping software wrapped by QIIME. We will measure within-sample biodiversity (alpha diversity) based on these OTUs using whole-tree phylogenetic diversity⁵⁶ and the Greengenes reference phylogeny. To quantify

differences in microbial carriage and composition between and within subjects over time, we will calculate the UniFrac distance [PMID: 20827291] between all pairs of samples. UniFrac is a measure of the fraction of the evolutionary tree relating all observed taxa that is not overlapping between two samples. To visualize these within- and between-subject differences (beta diversity) and to obtain principal components for subsequent statistical testing, we will perform dimensionality reduction using principal coordinates analysis. To enable tests for shifts in the relative abundance of both broad and specific bacterial taxa with respect to the host factors mentioned above, we will collapse the reference-based OTUs according to taxonomy at the genus and phylum levels using QIIME. This will produce culture-independent fractional observation counts of bacterial taxa in all samples.

We will test for overall differences in microbiome composition between short-course and standard-course antibiotics. To test for associations between individual bacterial taxa and these groups, we will perform non-parametric Mann-Whitney U tests. We will perform a similar test for association of microbiome biodiversity with treatment and between-sample diversity as well as gammaproteobacteria relative abundance.. In all cases the significance of association will be determined after correcting for multiple comparisons using false discovery rate.

Subpopulation Analyses: Treatment effects for the primary and secondary outcome measures will be estimated as differences between proportions and compared for subpopulations defined by age groups, febrile or non-febrile UTI (at original UTI diagnosis), and type of originally prescribed antibiotic. First, proportions will be tabulated as two-sample comparisons and chi-square tests for treatment differences in the outcomes within subgroups will be calculated. Factors where significant differences are observed will be further assessed using logistic regression analysis, assuming that the logistic model fits the data. Goodness of fit test will be reported for model checking. Treatment-by-subpopulation interactions will be tested using likelihood ratio tests. The power of these comparisons is expected to be low for both primary and secondary endpoints. The study is only likely to detect marked differences in treatment effects in these subpopulations.

Safety Analysis: Safety in this study is related to efficacy. Safety will be evaluated by the collection and analysis of data on SAEs, clinical laboratory tests, pain assessments, and concomitant medications. The investigator is responsible for reporting all SAEs that are observed or reported up, regardless of their relationship to study product. Serious adverse events and abnormal laboratory (if available) results will be compared by treatment arm, with statistical tests for differences in proportion of subjects with serious adverse events between study arms.

Missing Data: Several procedures will be used to conduct data analysis when data for either outcomes or covariates are missing. The first step will be to assess the extent and pattern of missing data. If data are missing for only a few cases, then data analysis will be conducted only on study participants with complete data. However, when such a strategy would result in loss of data from a substantial proportion of participants or would lead to biased or inaccurate results, then some form of imputation will be performed. The form of imputation used will depend on the nature of the data that are missing.

Attrition and Loss to Follow-up: It is expected that loss to follow-up will be minimal in this study. Because the study is of short duration, we are hopeful that we will be able to follow virtually all subjects to study completion. However, some study participants may withdraw consent or may not return for the follow-up visits to determine the primary endpoint. Other participants may not have the endpoint determined due to problems with specimens or laboratory processing. We anticipate that these factors may reduce the sample size by as much as 10%. Thus the sample was increased by approximately 11% to offset this sample size reduction. Note that study participants who disrupt or discontinue study treatment will continue with follow-up and have the study endpoints assessed, and will be included in the ITT analysis.

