If no exclusion criteria are met, the Study Coordinator will attempt to contact the parent(s)/guardian(s) by phone. The Study Coordinator will read an IRB approved telephone script, and obtain verbal consent from the parent(s)/guardian(s) for screening before proceeding with a brief symptom questionnaire to determine whether the child

experienced any UTI symptoms prior to the diagnosis that were not captured in the EHR. Once obtained, the verbal consent will be documented as per local institutional policy. The Study Coordinator will also explain the study protocol and describes the inclusion/exclusion criteria. The Study Coordinator will answer any questions and concerns the parent/guardian may have.

If it appears that a patient may be eligible based on hematology results and medical record review, the Study Coordinator may contact the parent(s)/guardian(s) by phone before urine culture results have been received. The Study Coordinator will call the parent(s)/legal guardian(s) again once culture results are received to inform them of their child’s eligibility status. Patients with cultures that do not meet inclusion criteria will be instructed to continue with initially prescribed antibiotic unless otherwise advised by the prescribing clinician.

If the patient has returned a positive culture, and the parent(s)/legal guardian(s) are still interested and believe their child meets the study eligibility criteria, the Study Coordinator will schedule the Enrollment Visit for a time before the child starts the sixth day of the initial antibiotic therapy. The enrollment visit may proceed even if urine culture sensitivities are still pending at the time of the visit. However, if final sensitivities show that the organism is resistant to the initially prescribed antibiotic, the subject is no longer eligible and should be excluded (or discontinued if the child was already enrolled). Staff will instruct the parent(s)/guardian(s) to continue with the initially prescribed antibiotic unless otherwise advised by the prescribing clinician.

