16.6 Protocol Deviations

A protocol deviation is any noncompliance with the clinical trial protocol, Good Clinical Practice, or protocol specific Manual of Procedures. The noncompliance may be on the part of the subject, the investigator, or the study site staff. If study staff is unable to contact a subject requiring the day 5/6 contact before the subject starts the study product on day 6, it will be categorized as a protocol deviation.

All protocol deviations will be reported to DMID within five working days of identification of the protocol deviation, or within five working days of the scheduled protocol-required activity. All deviations from the Protocol must be addressed in the Subject Source Documentation. The documentation should include the reasons for the deviation and all attempts to prevent or correct them. Protocol deviation reports will be submitted as required by site IRBs.

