4.2.6 Safety Analysis

Safety will be evaluated by the collection and analysis of data on (S)AEs. All (S)AEs will be reported, regardless of their relationship to study product (*Table 24 in Section 7.1*). The number of subjects with adverse events and the number of adverse events will be reported by body system and by treatment arm (*Table 24A-B in Section 7.1*). (S)AEs results (the number of subjects with adverse event and the number of adverse events) will be compared by treatment arm, with statistical tests for differences in proportion of subjects with serious adverse events between study arms. These analyses will use the ITT population and two-sided tests with significance level of 0.05 (*Table 25A in Section 7.1*).

Missing Data: Initially we will assess the extent and pattern of missing data using frequencies and cross-tabulations. If data are missing for only a few cases (5% or less), then data analysis will be conducted only on study participants with complete data. However, when such a strategy would result in loss of data from a substantial proportion of participants (i.e., 20%) or would lead to biased or inaccurate results, then sensitivity analysis or some form of imputation will be performed. The form of

imputation used will depend on the nature of the data that are missing. If data are missing for primary endpoint (treatment failure), frequencies for missing data by center, patient characteristic (clinical and demographic), and medication used will be examined. If there are significant associations of missingness with any of these characteristics, we would consider intent-to treat analysis with imputation methods such as regression technique, hot-deck, or best/worst case (for binary outcomes) and choose the one that would be most appropriate for type of missing data pattern (missing at random). If there is partial follow-up, that partial data might allow us to do an imputation. The imputation will be employed if there is a clear evidence of bias due to missing data. Sensitivity analyses will be performed to assess how sensitive results are to reasonable changes in the assumptions that are made for missing data.

To be considered evaluable a child must meet (a) below and one of (b) , (c) or (d):

(a) have taken study medication, AND;

(b) complete the Test of Cure visit, OR;

(c) have prior evidence of a treatment failure;

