5.1 Tables

▪ Definition of populations

- **Population 1:** All subjects taking at least one dose of study treatment between Day 6 and Day 10 who have been evaluated for treatment success at TOC or have failed prior to TOC (ITT population)
- **Population 2:** The enrolled subjects who were adherent to their assigned study regimen and completed more than 80% of the prescribed dose between Day 6 and Day 10 (per-protocol population)
- **Population 3:** Subjects in population 2 who did not experience a treatment failure.
- **Population 4:** Subjects in population 2 who have a stool sample at TOC visit. Some treatment failures will not have a sample collected at TOC because they failed prior to TOC. Treatment failures without the sample at TOC would be excluded from population 4.

▪ Definition for a subject having primary endpoint

The primary endpoint of this study is the proportion of children experiencing treatment failure (symptomatic UTI) at the TOC visit (Day 11-14).

▪ Data handling

- Treat blanks and “.” as missing unless specified otherwise.

6. References

1. [name] R, Chan E. A meta-analysis of randomized, controlled trials comparing short- and long-course antibiotic therapy for urinary tract infections in children. *Pediatrics*. May 2002; 109(5):E70-70.

7. Appendices

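### The per-protocol set has no eligibility condition, so children found late to have no confirmed index UTI or a resistant organism stay in both analyses; the effect is probably small and the repair is cheap

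*Protocol*

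**What the plan says.** **Per-protocol set.** Protocol 12.4: "the per-protocol analysis would include only subjects who were adherent to their assigned study regimen and completed 80% or more of the prescribed dose". SAP 5.1, Population 2: "The enrolled subjects who were adherent to their assigned study regimen and completed more than 80% of the prescribed dose", counted over Days 6 to 10. SAP 4.2.2 uses the same rule. None of the three mentions the entry criteria. Populations 3 and 4 are subsets of Population 2.

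**ITT set.** Protocol 12.4 takes "All subjects taking at least one dose of study drug(s) who have been evaluated for treatment success at TOC visit", plus those who failed earlier. SAP Population 1 matches it.

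**Evaluability.** The rule printed at the end of SAP 4.2.6 begins "To be considered evaluable a child must meet (a) below and one of (b) , (c) or (d". Its conditions are study medication taken, plus a completed visit or an earlier failure. Eligibility is not among them.

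**Related provisions.**
- Protocol 11.1: "Eligibility will be confirmed for 100% of subjects".
- Protocol 8.1: "The enrollment visit may proceed even if urine culture sensitivities are still pending at the time of the visit". A later resistant result leads to exclusion, or to discontinuation if the child is already enrolled.
- Protocol 16.1 says the SAP will cover definitions of eligibility and the planned reasons for leaving children with data out of an analysis. The SAP contains no eligibility-based exclusion.

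**The concern.** In a non-inferiority trial, a child whose outcome does not depend on treatment in Days 6 to 10 adds about the same failure rate to each arm and shrinks the observed difference. The ITT analysis keeps such children by design. The per-protocol analysis is the one planned analysis of the primary endpoint that could leave them out, and as defined it does not.

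Two kinds of child fit this description:
- **No confirmed index UTI** under the Protocol Section 3 definition. There is no infection for the longer course to finish treating.
- **An organism resistant to the initial antibiotic** (exclusion 3), reported too late to stop study product. The drug did not cover the organism, so five more days of it should matter little.

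Monitors verify eligibility for every child, but no analysis rule uses the result. Any exclusion made later would be post hoc.

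**Working it through.** **1. The plan's own sample size.** Inputs from SAP 3.2: failure 5% in both arms, margin 5 points, one-sided alpha 0.05, power 90%.

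n per arm = (1.645 + 1.282)² × (0.05×0.95 + 0.05×0.95) / 0.05² = 2.926² × 0.095 / 0.0025 = 325.4, which rounds up to 326. The SAP states 326. The 80% power figure of 235 also reproduces. The sample size is not in dispute.

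**2. Dilution model.** Inputs:
- 336 per arm, half of the protocol's 672 evaluable (Protocol Section 5). A real per-protocol set would be somewhat smaller.
- Eligible children exactly at the margin: 5% standard, 10% short course.
- Ineligible children: 5% in both arms (assumption).
- Share ineligible, x: not in the documents, so varied from 0 to 10%.

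Formulas:
- p0 = 0.05; p1 = (1−x)×0.10 + x×0.05
- SE = √[(p0(1−p0) + p1(1−p1))/336]
- P(wrongly meeting the margin) = Φ[(0.05 − (p1−p0))/SE − 1.645]

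Example, x = 5%: p1 = 0.0975, difference 0.0475, SE = 0.02008. Then 0.0025/0.02008 = 0.124, and Φ(0.124 − 1.645) = Φ(−1.520) = 6.4%.

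| Share ineligible | Expected difference (points) | False non-inferiority |
|---|---|---|
| 0% | 5.00 | 5.0% |
| 1% | 4.95 | 5.3% |
| 2% | 4.90 | 5.5% |
| 3% | 4.85 | 5.8% |
| 5% | 4.75 | 6.4% |
| 10% | 4.50 | 8.2% |

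**3. Sensitivity.** The common failure rate matters little. With 0% failure in ineligible children, the results at 5% and 10% ineligible are 6.5% and 8.3%. Exact binomial enumeration, with ineligible children at 5% in both arms, starts from 5.5% and gives 7.0% and 8.9%. The rise is about the same.

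**4. Removing these children.** The error returns to 5.0% in the per-protocol analysis. Power at 5% versus 5% is Φ(0.05/√(0.095/n) − 1.645): 90.8% at n = 336, 90.3% at n = 329 (2% removed) and 89.5% at n = 319 (5% removed).

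**5. When a resistant child stays in.** Study product starts on Day 6, and 80% of five days is reached at about the end of Day 9. A child discontinued before then falls below the dose threshold and leaves the per-protocol set, though Protocol 12.4 (Attrition) keeps discontinued children in follow-up and in ITT. Only a result reported after that point, or not acted on, leaves the child in both sets.

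**The case against.** **Conduct rules already do most of the work.** This stands. Screening reviews the laboratory and medical records, and the Enrollment Visit is scheduled on a positive culture (Protocol 8.1), so an unconfirmed index UTI requires a screening error. Only sensitivities may be pending, and a resistant result leads to exclusion or discontinuation. Entry failures are withdrawn before any study dose (Protocol 6.4.3 and 9.1) and enter neither set. Investigators may also discontinue a child for a protocol violation (6.4.3).

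**The analysis is supportive.** This also stands. Protocol 4.2.1 and 12.4 and SAP 4.2.2 make ITT primary. The label on shell Table 4 in SAP 7.1 does not override them. Secondary endpoints use two-sided tests of a difference, where dilution does not raise false positives. Most subgroup tables use Population 2 or its subsets, but shell Table 18 uses Population 1.

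**Not every ineligible child dilutes.** A reader might infer that every entry violation pulls the difference toward zero. The documents do not support that.
- Protocol 16.6 treats a child not reached "before the subject starts the study product on day 6, it will be categorized as a protocol deviation". If that child already had fever or symptoms, infection may be active, and Protocol 2.3.1 presents clinical improvement as what mitigates the short-course risk. Such children could widen the difference. In the same model, 3% of them failing at an assumed 10% versus 20% lowers the chance of meeting the margin from 5.0% to 4.3%; at 10% versus 30% it is 3.1%. Removing them would then favour non-inferiority. Where the contact was missed, the planned source of the information is also absent.
- For a second uropathogen, a Day 6 dose already taken, excluded anatomy or high-grade VUR, nothing in the documents implies equal failure in both arms. The difference could move either way.

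**Conclusion.** The gap holds for two groups: children without a confirmed index UTI, and children whose resistant organism is reported after about 80% of study doses. Neither document removes them from the per-protocol set, although eligibility is verified for every child and Protocol 16.1 says the SAP will set out planned exclusions.

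The size depends on an unknown share. At 1% to 3% the false non-inferiority rate is 5.3% to 5.8%; 6.4% and 8.2% require 5% and 10% ineligible. Given the conduct rules, the low end is more plausible. These figures assume equal failure in both arms among ineligible children and a true difference exactly at the margin.

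A reader might also infer that the primary result is wrong and that the fix corrects it. It does not: the ITT set and its error rate stay as they are. What improves is the per-protocol check and the analyses built on Population 2.

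**What to change.** In Protocol 12.4, SAP 4.2.2 and SAP 5.1, redefine Population 2 as Population 1 children who:
1. met the adherence rule;
2. had a confirmed index UTI under the Protocol Section 3 definition; and
3. had an organism not resistant to the initial antibiotic (exclusion 3).

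Classify each child from the eligibility verification already planned for all subjects, blind to arm and outcome, before database lock. Report the number excluded by arm and reason. Do not extend the list to other violations on the ground that they dilute the difference.

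When editing, settle the dose threshold as well. The protocol says 80% or more, while the SAP has "completed more than 80% of the prescribed dose between Day 6 and Day 10 (per-protocol population"). Both adherence tables list exactly 80% of doses, such as four for cefixime, which is dosed once daily for five days.

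The cost is a wording change and a blinded listing; no new data are needed. The per-protocol set becomes slightly smaller, costing about 0.5 points of power at 2% removed (90.8% to 90.3%) and 1.3 points at 5% removed (to 89.5%).
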